The 344 caregivers enrolled in the RCT for a 12-month follow-up will complete an intervieweradministered baseline survey (by phone, video or online) and phone- or web-based follow-up surveys at 7 days, one month, 3 months, and 12 months after the index visit. The 50 additional male caregivers enrolled in the RCT for a 3-month follow-up will complete an interviewer-administered baseline survey (by phone, video or online) and phone- or web-based follow-up surveys at 7 days, one month, and 3 months after the index visit. Surveys will elicit self-reported data in the following domains: caregiver status, caregiver sociodemographic characteristics (e.g., age, race/ethnicity, sex and gender), caregiver-reported care recipient demographics (e.g. age, race/ethnicity), employment, household composition, income and insurance status, stage of dementia of the care recipient; psychosocial characteristics (e.g., caregiver self-efficacy, unmet health-related social and caregiving needs, burden, depression, stress and well-being); behaviors (e.g., use of resources, use of the Community Resource Finder, resource information sharing, activation of the Community Resource Specialist); health and healthcare use (e.g., physical health and healthrelated quality of life and healthcare utilization); and healthcare experience (e.g., satisfaction with care, stigma). Caregivers will be asked a limited number of questions as proxy for the care recipient to assess: well-being, community resource needs and use, health and healthcare utilization.

If needed to supplement healthcare utilization data, we will obtain health insurance claims for the participant. The informed consent/assent process will inform study participants of the rationale for accessing these data and request participants' permission to do so.

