Certain survey data elements collected in the REDCap database will be sent securely to NowPow, a systematic resource referral platform, to generate the HealtheRx and to Mosio, a secure text messaging platform, to facilitate the proactive text messaging protocol and manage survey scheduling and reminders for all participants. Elements of PHI sent to NowPow to generate a personalized HealtheRx include: participant name, participant home address, date of birth and other non-PHI data elements. Data will be securely transferred from REDCap to NowPow through a custom secure integration created by the Center for Research Informatics. In addition to other non-PHI data elements, respondent address is necessary to better tailor the community resource information provided on the personalized HealtheRx. Elements of PHI sent to Mosio to facilitate the text messaging protocol and scheduling/reminders include: participant name, telephone number and date of enrollment in the study.

Metadata generated by use of the NowPow system will be provided to the research team via Globus for secure file transfer on a regular basis (see documentation below). NowPow is a company serving dozens of blue chip health systems using rigorous data protocols and therefore operates its technology in a manner that meets the strict HIPAA and security criteria standards of these organizations.

Qualitative interviews will be audio recorded and transcribed. Qualitative interview audio recordings will be transcribed by Amazon Web Services (AWS) Transcribe. AWS Transcribe has been reviewed and approved by the BSD Information Security Office and deemed to be HIPAA-compliant. Interviews will be de-identified upon transcription.

Because PHI will be accessed and collected for this program of research, there is a risk of loss of confidentiality. To protect confidentiality, we will implement a plan to protect data in all its forms

from improper use and disclosure using HIPAA compliant policies and procedures; see Section N. Procedures to Maintain Confidentiality for more information.

Use of Globus for File Transfer

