REDCap will integrate electronically with the Mosio texting platform (www.mosio.com) to facilitate the text message protocol for human subjects in the intervention group and manage survey scheduling and reminders for all participants. To this end, REDCap will push the subject's name, telephone number and date of enrollment to Mosio via REDCap's secure API. Mosio provides a secure messaging and data storage environment and has been approved for use by the University of Chicago Information Security Office. Only approved researchers in the [name] Lab will have access to data stored by Mosio and will have the ability to securely download data directly to computers within the Ob/Gyn network.

All hard copies of project materials will be stored in locked file cabinets in locked offices at University of Chicago. Servers in the University of Chicago Department of Ob/Gyn are protected through a combination of a Microsoft-based firewall technology and the physical barrier of a Linksys router that is installed between the server and its internet connection. Laptop computers used to collect data will be encrypted and password protected. All data transmitted to secure servers will be encrypted. Analytic files will either be de-identified prior to analysis or limited to the minimum amount of data necessary to accomplish the intended research purposes per the HIPAA Privacy Rule. Any analytic datasets will limit the use or disclosure of PHI to the minimum necessary, if any at all, to accomplish the intended research purposes. Only IRB-approved researchers on this protocol will have access to data. These controls meet or exceed the strictness

of practices legislated and enforced by the University of Chicago Biological Sciences Division and hospitals for protected health information.

Procedures are in place to ensure confidentiality and provide informed consent as discussed above. Numeric coding of surveys/interviews and secure containment of files that link participant's responses from PHI will also minimize this risk. Finally, the [name] Laboratory will provide a contact phone number that will be included on all study correspondence and forms. The purpose of this phone number is to provide respondents with a single number to call if they have questions about any aspect of the study.

O. Bibliography

Bibliography included in online submission, View 8.1.

P. Recruiting methods

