The baseline survey will be administered following randomization by a trained interviewer. All caregivers will receive usual care. Participants will be blinded to the arm to which they are randomized. For caregivers randomized to the intervention arm, CRx-D will be delivered by the interviewer. Follow-up phone surveys will be conducted using computer-assisted personal interviewing (CAPI) at 7, 30, 90 days and 12 months post-enrollment. To maximize retention, a brief check-in will be conducted at 180 days and we will use text messaging and phone calls monthly between surveys to verify contact information and to schedule and remind participants about upcoming surveys. Intervention group participants can also text, email or call the CRx-D resource specialist for resource support throughout the follow-up period.

We will conduct two waves of baseline and 1 week follow-up pre-testing (Y1Q3), each with 5 ADRD caregivers with 1 or more unmet HRSNs and 5 ADRD caregivers with 0 unmet HRSNs (20 total with the two waves) to ensure survey quality and minimize risk of measurement and CAPI error. Table 1 summarizes example measures, sources and planned time points for collection. Dynamic factors will be assessed at appropriate intervals (e.g., during the last 30 days or in the interval since the last survey).

The primary outcome for Aim 1 will be assessed using the 4-item self-efficacy sub-domain from the 2015 Caregiver Dementia Care and Self-Efficacy Survey developed by Jennings et al (NIA-5P30AG028748, CMS-1C1-12-0001). We selected this relatively new measure because it is, to our knowledge, the only available measure validated specifically for ADRD caregivers that assesses self-efficacy for accessing services.

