To fully leverage the longitudinal data, generalized linear mixed-effects models (GLMM) will be fit with particular interest in the time (7, 30, 90 days and 12 months post-enrollment) by study arm interaction; baseline values will be included as a covariate. Based on this model, appropriate contrasts to test the intervention effect at specific time points (e.g., 12 months) will be constructed. These contrasts will permit examination of early versus late intervention effects, valuable information for future iterations of this and other ADRD caregiver self- and family management interventions. GLMM can be used for continuous (e.g., mean caregiver self-efficacy for providing care score, patient satisfaction score, stigma score), ordinal (e.g., physical health of PWD by proxy) or binary (e.g., resource use, resource sharing) outcomes. Models will include covariates moderately associated with the outcome to remove differences attributable to baseline covariates and increase precision of the estimate of the treatment affect. Latent growth curve modeling is a viable alternative to GLMM and will be explored when sufficient variability in the distributions of patterns of outcomes by time points exist (e.g., with the binary outcomes there will be a limited number of potential patterns).

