Hypothesis 2c. Among ADRD caregivers with no unmet HRSNs at baseline, those randomized to the CRx-D intervention will demonstrate a lower likelihood of developing an unmet HRSN. In addition, they will exhibit a higher likelihood of sharing resource information with others compared to those randomized to usual care.

**Strategy, Timeline, Methods, and Key Measures:** Aim 2 will utilize RCT data (collected as described in Aim 1) from ADRD caregivers with and without unmet HRSNs. For Aim 2, the primary outcome of interest is satisfaction with care. Satisfaction will be assessed 7 days post-discharge from the caregiver's primary care visit using the Patient Satisfaction Questionnaire 18-item short form (PSQ-18). The PSQ-18 is widely used in research and shows internal consistency with the long form of the PSQ, an 80-item survey developed in 1976. The 18 items are grouped into 7 domains; each domain is scored separately (there is no overall score). The general satisfaction sub-scale of the PSQ (2/18 questions) is the most relevant PSQ domain for our study.

To assess stigma, we will use the Discrimination in Medical Settings Scale (DMS). The DMS was adapted from the Everyday Discrimination Scale for medical settings and has been tested for reliability and validity among African Americans. It includes 7 items, each scored on a 1 to 5 scale to generate a mean overall score.

Using the same transition model approach described for Aim 1, we will study the impact of the intervention on state changes in unmet needs specifically among caregivers without unmet needs at baseline. This approach will fill a gap in knowledge about the joint incidence of unmet HRSNs and ADRD caregiving needs over time.

Lastly, among those assigned to the intervention group, we will examine caregivers' propensity for sharing information about resources, comparing a) those with and without unmet HRSNs at baseline and b) among those without baseline unmet HRSNs, by study arm. Based on Maslow's Theory of Human Motivation, we hypothesize higher caregiving self-efficacy and well-being rates at 12 months among caregivers who shared resource information with others and that the effect will be highest for caregivers with unmet baseline HRSNs.

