**Analysis and Sample Size Justification** Physician concern about negatively impacting patient satisfaction or causing stigma are barriers to intervening to address unmet needs. To address these, we hypothesize that satisfaction with care will not be significantly diminished among caregivers randomized to CRx-D compared to those randomized to usual care. Aim 2 analyses will include all caregivers enrolled in the trial (N=344).

We will use the analytic approach described for Aim 1. Here, we discuss analytic issues unique to Aim 2. To facilitate ease of interpretation of the primary outcome, we will linearly rescale the composite score for the PSQ-18 subdomain of general satisfaction (questions 3 and 17). Five possible responses for each of the two items are scored 1 to 5; with a higher score equating to higher satisfaction. Scores will be transformed using the formula: y= 100 \* (x-a)/(b-a) where y=the transformed score, x=the original score, a=the minimum possible score and b=the maximum possible score. Transformed items will be averaged to generate the composite score (range 0-100). Of particular interest for the non-inferiority hypothesis (H2b) will be the confidence interval for the difference (usual care - CRx-D) and whether or not the upper limit of the confidence interval exceeds the non-inferiority margin. Of note, superiority of the intervention with respect to stigma, unmet needs and other outcomes will also be tested as this can be done without penalty. Caregiver satisfaction will be measured at 7 days following the baseline outpatient visit; no longitudinal analyses will be conducted for this outcome. Typically, analyses of patient satisfaction data adjust for case-mix (age, education and general health status); this will be feasible, but given the randomized design and single-site analysis, adjustment should not be necessary. In addition,

to determine whether there are substantial differences in the intervention's effect on ADRD caregivers with unmet HRSNs compared to ADRD caregivers without unmet HRSNs, the intervention by unmet HRSNs interaction will be tested. As in Aim 1, we will examine for differential intervention effects on primary and secondary outcomes among racial and ethnic groups, and by sex, using effect modification analyses. Some analyses will be restricted to the group without HRSNs (N=172) to provide a more complete assessment of the impact of the intervention on this group (e.g., incidence of unmet HRSNs over time).

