#### **Measures Used**

#### Satisfaction with Care

Satisfaction will be assessed 7 days post-discharge from the caregiver's ambulatory visit using the Patient Satisfaction Questionnaire 18-item short form (PSQ-18). The PSQ-18 is widely used in research and shows internal consistency with the PSQ long form, an 80-item survey developed in 1976. The 18 items are grouped into 7 domains; each domain is scored separately (there is no overall score). The general satisfaction sub-scale of the PSQ (2/18 questions) is the most relevant PSQ domain for our study.

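### Does the Aim 2 satisfaction survey need a single stated clock, and a separate analysis for caregivers who had no visit of their own?

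*SAP*

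**What the plan says.** **Visit clock.**
- Aim 2 SAP, Satisfaction with Care: "Satisfaction will be assessed 7 days post-discharge from the caregiver's ambulatory visit".
- Overall SAP, Aim 2 measures: "Satisfaction will be assessed 7 days post-discharge from the caregiver's primary care visit".
- Overall SAP, Aim 2 analysis: "Caregiver satisfaction will be measured at 7 days following the baseline outpatient visit".
- Final protocol, section C: "follow-up surveys at 7 days, one month, 3 months, and 12 months after the index visit". The same section describes the index visit as the primary care visit, or the end of a telemedicine visit, at which the intervention is started.

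**Enrollment clock.**
- Overall SAP, Aim 1 RCT strategy, places the follow-up surveys "at 7, 30, 90 days and 12 months post-enrollment".
- The mixed-model time points, repeated in the Aim 1 and Aim 2 plans, are "7, 30, 90 days and 12 months post-enrollment".

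**Scheduling data.** Final protocol, sections F and N, list what goes to the messaging platform: "scheduling/reminders include: participant name, telephone number and date of enrollment in the study" and "REDCap will push the subject's name, telephone number and date of enrollment to Mosio via REDCap's secure API".

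**Population.** The inclusion criteria in section H of the final protocol do not ask for a visit of the caregiver's own. Section G describes usual care for accompanying caregivers who are not patients. Section P allows for recruiting non-patients, partly through flyers, social media and research websites. The Aim 2 SAP analyses all 344 enrolled caregivers.

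**The concern.** Satisfaction with care is the Aim 2 primary outcome and is tested for non-inferiority. In the 2018 grant application, from which much of the SAP is copied, caregivers were to be enrolled in the waiting room, so visit and enrollment coincided. The final protocol separates them. Sections M and P allow e-consent, delivery and survey within a week of the visit, and consent before or after a telemedicine visit. The Aim 2 SAP adds later clarifications in brackets. One of them gives the discrimination scale a day 7, without an anchor, while the satisfaction timing was left alone.

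For a caregiver with no visit of their own, the stated rule cannot be applied, and no text says which care they are rating. In a non-inferiority test, ratings unrelated to the encounter could pull the arms together and make a true loss of satisfaction harder to see.

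**Working it through.** **1. The plan's own figure.** Inputs from the Overall SAP and the Aim 2 SAP, Sample Size: margin 7.6, SD 25, one-sided alpha 0.025, power 0.8, allocation 1:1.

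n per arm = 2 × (1.96 + 0.842)² × 25² / 7.6² ≈ 170, or 340 in total, against 344 stated. At 172 per arm, SE = 25 × √(2/172) = 2.696 and power = Φ(7.6/2.696 − 1.96) = 80.5%. The figure reproduces, and the timing question does not touch it.

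**2. How far apart the clocks can be.** Let d be the days from visit to enrollment. Sections M and P permit roughly d = −7 to +7.
- Enrollment clock: the survey falls 7 + d days after the visit.
- Visit clock: the survey falls 7 − d days after enrollment.

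| d | Visit to survey, enrollment clock | Enrollment to survey, visit clock |
|---|---|---|
| −7 | 0 | 14 |
| 0 | 7 | 7 |
| +3 | 10 | 4 |
| +7 | 14 | 0 |

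The end rows are arithmetic limits. With same-day enrollment the clocks agree.

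**3. Which clock was used.** The messaging-platform fields seem to point to enrollment. But the pretest protocol, included in the same document, lists the same fields in its sections F and N, while its section C runs the surveys from the index visit. The field list is therefore compatible with a visit clock and settles nothing. The enrollment wording in the SAP is grant-era text, from when the distinction did not matter. The final protocol, approved in November 2023, uses the index visit. The documents lean towards the visit without proving it.

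**4. Whether the choice affects the comparison.** The Overall SAP randomizes immediately after enrollment, and no text gives the arms different survey clocks. It also rules out longitudinal analysis of satisfaction. The Aim 2 SAP, Additional Information, gives the model as outcome on treatment indicator alone. Survey day does not appear in it, so renaming the anchor changes no estimate.

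**5. Caregivers without a visit: an illustration.** Let f be their share (assumed, since the documents give none). Suppose that their true difference is zero and that everyone else's deficit equals the margin. The chance of declaring non-inferiority is then Φ(7.6f/2.696 − 1.96). If they are left out instead, power is recalculated with 172(1 − f) per arm, and the half-width is 1.96 × 25 × √(4/N), with N rounded to an even total.

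| f | Declares non-inferiority if kept | Power if excluded | N | 95% half-width |
|---|---|---|---|---|
| 0 | 2.5% | 80.5% | 344 | 5.28 |
| 10% | 4.7% | 76.3% | 310 | 5.57 |
| 20% | 8.1% | 71.3% | 276 | 5.90 |
| 30% | 13.3% | 65.5% | 240 | 6.33 |

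The second column counts as an error only for the subset with a visit. Across all enrolled caregivers, which is the population the plan names, the true deficit in that scenario is 7.6(1 − f), which lies inside the margin.

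**The case for a change.** The best case for acting is that the conflict sits in the primary outcome, could be settled with a sentence, and has a counterpart in the population. The recruitment routes for non-patients were not created only for the 50 additional men, who are outside the 344. The pretest protocol, section P, already foresaw non-patients, flyers and social networks for the full trial, and the amendment log dates the research-website route to June 2021, before the October 2022 supplement. If such caregivers were numerous, the table above shows that they could matter for the subset with a visit.

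The conflict of anchors stands, and so does the missing rule for a caregiver without a visit. The rest is weaker.
- The Overall SAP describes eligible subjects as patients seeking care at the center. In section P of the final protocol, the first route recruits from the clinic schedule, and the second asks whether the contact is also a patient and returns around that person's own visit. The provision for accompanying persons depends on in-person recruitment resuming. This suggests a small share, though no count is given.
- No text says that the two general satisfaction items ask about one particular visit. The SAP benchmarks them against a population-based sample, which suggests that they need not. The dilution argument depends on that unsupported link.
- Whether a caregiver had a visit before enrollment is settled before randomization, so the share should be similar in the two arms.

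**Conclusion.** No change to the plan is needed. The anchors do conflict, by up to about a week in either direction, and the documents do not say which was used. This is missing detail inherited from the grant text. The analysts know when each survey was fielded and can state the anchor when they report the result.

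A supportive analysis limited to caregivers with a visit of their own offers no demonstrated gain. The documents do not show that visit status was recorded in usable form. The data had already been analyzed, so the estimate would be post hoc. It would also be less precise (half-width 5.57 to 6.33 against 5.28, for assumed exclusions of 10 to 30%) and could not replace the 344-caregiver result.

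This rests on two points: that both arms were surveyed on the same clock, which nothing in the documents contradicts, and that caregivers without a visit are few, which the recruitment text suggests but does not quantify. No bias between arms and no attenuation has been shown.

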### **Experiences of Discrimination**

To assess stigma, we will use the Discrimination in Medical Settings Scale (DMS) [and it will be assessed on day 7]. The DMS was adapted from the Everyday Discrimination Scale for medical settings and has been tested for reliability and validity among African Americans and used in studies of Korean American and American Indian women. It includes 7 items, each scored on a 1 to 5 scale to generate an overall score [range 7-35, higher scores indicating more frequent discrimination].

#### Sample Size

Aim 2 analyses will include all caregivers enrolled in the trial (N=344). The non-inferiority margin of 7.6 points is less than half of the standard deviation for mean transformed general satisfaction scores in a population-based sample (e.g., male [mean=65, SD=23], female [mean=64, SD=24]); half a standard deviation is considered a minimally important difference. [Calculations assumed power=0.8, one-sided alpha=0.025, and standard deviation=25]

### Analysis Plan

# *Aim* 1 Analytic Plan [Aim 1 analytic plan is included here because it was referenced in Aim 2 due to overlap)

To determine the impact of CRx-D on the highest risk group, Aim 1 analyses will focus on 172 caregivers with at least 1 HRSN. Descriptive statistics will be used to summarize, overall and by study arm, sociodemographic characteristics and primary and secondary outcomes at each measured time point. The mean, standard deviation, median, and inter-quartile range will be generated for continuous variables; frequency counts and percentages will be generated for categorical variables.

The main analyses will follow the principle of intent-to-treat, and include all 172 ADRD caregivers with at least 1 unmet HRSN in the study arm to which they were allocated.

To fully leverage the longitudinal data, generalized linear mixed-effects models (GLMM) will be fit with particular interest in the time (7, 30, 90 days and 12 months post-enrollment) by study arm interaction; baseline values will be included as a covariate. Based on this model, appropriate

contrasts to test the intervention effect at specific time points (e.g., 12 months) will be constructed. These contrasts will permit examination of early versus late intervention effects, valuable information for future iterations of this and other ADRD caregiver self- and family management interventions. GLMM can be used for continuous (e.g., mean caregiver self-efficacy for providing care score, patient satisfaction score, stigma score), ordinal (e.g., physical health of PWD by proxy) or binary (e.g., resource use, resource sharing) outcomes. Models will include covariates moderately associated with the outcome to remove differences attributable to baseline covariates and increase precision of the estimate of the treatment affect. Latent growth curve modeling is a viable alternative to GLMM and will be explored when sufficient variability in the distributions of patterns of outcomes by time points exist (e.g., with the binary outcomes there will be a limited number of potential patterns).

Potential moderators of the intervention effect (e.g., race, sex) will also be assessed by inclusion of a moderator by study arm interaction term. Although in the CRx-2 trial we saw no gender differences in outcomes, special consideration will be given to sex (as measured by self-reported gender) as a biological variable (moderator) and variation in intervention effects will be examined in accordance with NIH policy. In addition, based on preliminary evidence of similarity across race and ethnic groups from the CRx-2 trial, we hypothesize that the intervention effect will be similar and will analyze for dramatic departures from this outcome (e.g., whether the intervention has no or negative effect among non-Hispanic white caregivers versus a strong positive effect among AA/B caregivers) through effect modification analyses (e.g. testing race by intervention interaction). Also, we will use mediation analyses to identify factors that mediate the relationship between the study arm and the outcome of interest. Improved understanding of moderating and mediating factors will facilitate future improvements to the intervention. For example, if the relationship between intervention effect and caregiver burden at time t is mediated by self-efficacy at time t-1, as posited in our conceptual framework, future improvements might focus the intervention's messaging more explicitly on fostering caregiver self-efficacy.

## Aim 2

We will use the analytic approach described for Aim 1 [above]. Here, we discuss analytic issues unique to Aim 2. To facilitate ease of interpretation of the primary outcome, we will linearly rescale the composite score for the PSQ-18 subdomain of general satisfaction (questions 3 and 17). Five possible responses for each of the two items are scored 1 to 5; with a higher score equating to higher satisfaction. Scores will be transformed using the formula: y = 100 \* (x-a)/(b-a) where y=the transformed score, x=the original score, a=the minimum possible score and b=the maximum possible score. Transformed items will be averaged to generate the composite score (range 0-100; [higher scores indicating greater satisfaction]). Of particular interest for the non-inferiority hypothesis will be the [95%] confidence interval for the difference (usual care - CRx-D) and whether or not the upper limit of the confidence interval exceeds the non-inferiority margin. Of note, superiority of the intervention with respect to [satisfaction or] stigma will also be tested as this can be done without penalty. Typically, analyses of patient satisfaction data adjust for case-mix (age, education and general health status); this will be feasible, but given the randomized design and single-site analysis, adjustment should not be necessary. In addition, to determine whether there are substantial differences in the intervention's effect on ADRD caregivers with unmet HRSNs compared to ADRD caregivers without unmet HRSNs, the intervention by unmet HRSNS interaction will be tested. As in Aim 1, we will examine for differential intervention effects on primary and secondary outcomes among racial and ethnic groups, and by sex, using effect modification

analyses. Some analyses will be restricted to the group without HRSNs (N=172) to provide a more complete assessment of the impact of the intervention on this group (e.g., incidence of unmet HRSNs over time).

